**[name], MSc, PhDc**

**Supervising Professor: [name]**

**ATHENS 2019**

# **Implementation of Enhanced Recovery After Surgery (ERAS) Pathways in Gynecologic Oncology**

## **Abstract**

### **Background**

Gynecological cancer is comprised of cancer of the female reproductive system, which includes the cervix, vulva, uterus, fallopian tubes, ovaries, and vagina [1]. The therapeutic approach to gynecological cancers involves surgical resection, with chemotherapy and/or radiation, and should always be scheduled and performed in specialized oncology centers [2] (European Society for Medical Oncology- ESMO, 2014).

Major gynecological oncology surgeries (MGOS) cause moderate to severe postoperative pain and discomfort [3]. Patients undergoing MGOS need a multimodal approach to postoperative pain management, which provides great analgesic results with minimal side effects.

Opioid regimens are commonly used in postoperative analgesia with often many side effects. In recent years, there has been a global effort to reduce the use of opioid regimens, in order to reduce their side effects (opioid-sparing multimodal analgesia).

Various alternative postoperative pain approaches have been studied that reduce the need for high doses of opioids postoperatively, such as the use of coxib and gabapentin (Alayed et al., 2014).

The last decade, the need to reduce the hospital stay (LOS) and the hospital cost have been developed new pathways of fast track surgeries, known as Enhanced Recovery after Surgery (ERAS) protocols. ERAS pathways have been reported to promote earlier recovery and be beneficial for patients.

ERAS pathways involve evidenced based approaches in three phases: preoperative, intraoperative and postoperative, by an interdisciplinary team including surgeon, anesthesiologist and perioperative nurse. The combination of these techniques reduces the postoperative stress response, relieves acute postoperative pain, promotes early feeding and mobilization, thus reducing LOS and hospitalization cost and increasing patient satisfaction (Barber & Van, 2015).

### **Aim**

The hypothesis of this theses was if the ERAS pathway could reduce the length of stay (LOS) in hospital for patients undergoing MGOS. The study aims to compare the effectiveness of ERAS protocol and the conventional non-ERAS clinical practice of recovery, of patients who will undergo MGOS.

### **Objectives**

The objectives of the present study comparatively in the two groups are:

#### **1. Hospital length of stay (LOS)**

Measuring how many days will stay in hospital for recovery. It is defined as the time frame from the day of operation to discharge from the hospital (unit: days)

#### **2. Pain levels**

Evaluation of analgesia and correlation of requirements with opioid analgesics; by recording of postoperative pain levels and the evaluation of the effectiveness of analgesic

treatment of patients. Using Numbered Pain Scale. As lower the number on pain scale as better the outcome.

### 3. Hospital Complications

The evaluation of postoperative complications such as bleeding, thrombosis and inflammation.

### 4. Mobilization

Mobilization time, which is defined as the time frame from the end of operation to the ability to walk without external assistance (unit: hours). Patients will perform a 6 minutes walking test.

### 5. Depression-Stress- anxiety

The evaluation of the presentation or not, of the patients 'depression, of the patients' emotional state (anxiety-depression) for their current state of health. Using HADS scale. Scores for each sub scale (depression and anxiety) are summed-up and range from 0-21. Values from 0-7 indicate normal levels, 8-10 are border values and from 11-21 are considered as pathologicales.

### 6. Readmission rate by 30 days after discharge of the hospital.

## **Method**

This is a randomized study.

The study will be carried out at a General Oncology Hospital of Athens.

Study population: The study sample will include patients with gynecological cancer who undergo tumor resection surgery, and they will be randomly divided into two groups.

Group A will include patients who will follow the ERAS protocol, and the group B will include patients who will follow conventional postoperative care.

Randomization: Based on the results of the pilot research, a power analysis will be performed and the final number of the sample with the hypotheses with a significance level of 0.05 will be determined.

Next, the total number of n patients in the study sample will be randomly divided into two groups in the two intervention categories A (ERAS) and B (Classical) with a fixed number of individuals each.

Data analysis:

The processing and statistical analysis of the data will be done using the software package IBM SPSS 21.0 (Statistical Package for Social Sciences). The level of statistical significance (value a), in all statistical tests, will be equal to 0.05. Thus, a value of  $p < 0.05$  will be considered statistically significant. The statistical analysis will include the following (Galanis 2015):

(a) Univariate analysis. Frequency distributions of the variables to study the values of each variable separately and independently of the others. The continuous variables will be expressed as mean (standard deviation), while the nominal variables as absolute (n) and relative frequencies (%).

(b) Variable analysis. Appropriate statistical controls will be used depending on the type and distribution of variables, such as e.g. the  $\chi^2$  (chi-square test), the t (student's t-test), the analysis of variance, the Pearson correlation coefficient, the Spearman correlation coefficient etc.

(c) Multivariate analysis. Multivariate linear and logistic regression models will be implemented to neutralize confusers.

Research tools: The numerical scale of pain will be used to assess the intensity of pain (Sarakatsianou, 2012).

The HADS scale (Michopoulos et al., 2008) will be used to assess patients' emotional state and is designed to assist in the assessment of anxiety and depression in patients in general hospitals.

For the collection of medical parameters, data will be collected from the anesthesia charts, the surgery minutes, the patient's personal file, the protocol data and from interviews with patients.

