### **Expected results from the research**

The present research is expected to assess the contribution of enhanced recovery after surgery programs and their benefits to both the patient individually and the health system in general. The importance of these programs is expected to emerge in the days of hospitalization, in postoperative pain, in perioperative stress and in the mobilization of patients who will have undergone major gynecologic oncological surgeries. In addition, conclusions will be drawn about the quality of life of women with gynecological cancer that will help health professionals understand the needs of these patients and their care. While, from the study of the complications and the estimation of the financial health expenses, for the patients with gynecological oncological problem who will undergo surgical treatment, it is expected that future measures will be taken to reduce and prevent the complications but also to minimize the health care expenses.

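### Does leaving the sample size to a power analysis of unspecified pilot results, with no length-of-stay difference or power stated, call for a change to the plan?

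*Combined protocol and SAP*

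**What the plan says.** All of the sample-size text is in the Randomization paragraph of the Method section. It says "Based on the results of the pilot research, a power analysis will be performed and the final number of the sample", taken with the hypotheses, "with a significance level of 0.05 will be determined". The next sentence says that "the total number of n patients in the study sample will be randomly divided into two groups", with a fixed number in each. The total stays as the symbol n.

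The Aim section supplies the hypothesis, which asks "if the ERAS pathway could reduce the length of stay (LOS) in hospital". Objective 1 defines LOS in days, from the operation to discharge. The section on expected results adds: "The importance of these programs is expected to emerge in the days of hospitalization". None of these gives a number of days.

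Of the usual inputs, the plan therefore states alpha (0.05) and lets LOS be inferred as the endpoint. It does not state the difference to detect, the SD, the power, the sidedness or the size of the pilot. It also does not say which pilot result enters the calculation. The pilot is mentioned nowhere else.

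**The concern.** A power analysis for two means needs a difference, an SD, a power and an alpha. Only alpha is given, and the sole named source for the rest is the pilot. A reader could conclude that the pilot's observed LOS difference will be used as the difference to detect.

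That rule is known to behave badly with small pilots. A pilot that overstates the benefit by chance leads to a trial that is too small and a quoted power that is not real. A pilot that understates it leads to an n that one hospital may be unable to recruit. There is also a point of principle: a pilot can estimate variability, but the LOS reduction worth detecting is a clinical and resource judgement. If no such figure is named, readers cannot see what the trial was built to find.

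**Working it through.** The plan states no sample size or power, so there is no figure to reproduce. The question is how much depends on the unstated rule.

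**Inputs.** From the Method section: alpha 0.05. Assumed: two-sided test, 1:1 allocation, 80% power, normal data, pilots of 10 to 100 per arm, true standardised effect d of 0.3, 0.5 or 0.8. LOS is usually skewed, so the figures are indicative.

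**Formula.** n per arm = 2(1.96 + 0.842)² / d² + 0.96, rounded up. The numerator is 2 × 7.851 = 15.70. At d = 0.5 this is 15.70/0.25 + 0.96 = 63.8, so 64 per arm.

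**Noise in the pilot effect.** The approximate 95% half-width is 1.96 × √(2/m) for m per arm: 0.88 at m = 10, 0.51 at m = 30 and 0.28 at m = 100.

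**One example.** With m = 20 the standard error is √(2/20) = 0.32. Suppose the truth is 0.5.
- A pilot estimate of 0.8, about one standard error too high, gives 15.70/0.64 + 0.96 = 25.5, so 26 per arm. True power by the normal approximation is Φ(0.5 × √(26/2) − 1.96) = Φ(−0.16), about 44%.
- A pilot estimate of 0.2 gives 15.70/0.04 + 0.96 = 393.5, so 394 per arm.

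**Reading A: the pilot's observed effect sets n.** Simulation with 200,000 pilots per setting; only pilots favouring ERAS go forward; no cap or floor on n. The middle columns are for a true effect of 0.5.

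| Pilot per arm | n per arm, 10th–90th percentile | Mean true power | Trials with power below 50% | Mean power at 0.3 | Mean power at 0.8 |
|---|---|---|---|---|---|
| 10 | 13–672 | 65% | 37% | 54% | 72% |
| 20 | 19–514 | 71% | 27% | 62% | 76% |
| 30 | 23–388 | 74% | 21% | 66% | 77% |
| 50 | 28–252 | 76% | 14% | 71% | 79% |
| 100 | 35–157 | 78% | 6% | 75% | 80% |

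If pilots with the wrong sign are kept and their effect is squared, the upper limits rise (to 875 per arm for a pilot of 20). A cap on n would cut them. With a floor of 30 per arm, mean power is 72% to 78% at 0.5 and 88% to 91% at 0.8.

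**Reading B: the pilot supplies only the SD, and the difference is fixed in advance.** At a standardised difference of 0.5, the 10th to 90th percentile of n is 39–92, 47–83, 50–80, 53–76 and 56–72 per arm for the same five pilot sizes. Mean power at the chosen difference is 77% to 80% for pilots of 10 to 30 per arm. The instability has largely gone.

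**What fixing the difference buys.** The power under Reading B is power at the chosen target. Suppose the target is 1.25 times the truth, so 0.625 against a true 0.5. Then n = 15.70/0.3906 + 0.96 = 41.2, so 42 per arm, and power is Φ(0.5 × √(42/2) − 1.96) = Φ(0.33), about 63% with the SD known. With the SD estimated from the pilot, simulation gives 60% to 61%. That is below every mean power in the 0.5 column under Reading A. A target 0.75 times the truth gives 93% to 96%. Fixing the difference yields a stable n and a visible target, but not assured power at the unknown truth.

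**The case for a change.** The strongest case for a change is that the gap exists on either reading. The difference, the power and the rule for using the pilot are not fixed before the pilot data are seen. The text permits the observed effect as input and names no other source for it. The arithmetic under Reading A is sound, and one rewritten paragraph would settle the matter.

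Part of this stands. The inputs are missing, and stating them would be good practice. A fixed difference also gives a steadier n and a target that readers can judge.

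Three parts do not carry the weight put on them. First, the harm belongs to Reading A, which the plan never states; a pilot SD is equally a pilot result. Second, it may be said that without a named difference a null LOS result could not exclude a useful reduction. The confidence interval for the LOS difference, set against a clinical threshold, answers that whatever the sample-size paragraph says. Third, there is no need to require that pilot patients be left out. The order of the two sentences already suggests that they are separate from the n randomised. If the pilot supplied only the SD, keeping patients randomised under the same protocol usually has little effect on type I error. The case would be less benign if the observed effect set n and those patients were then also analysed, but nothing in the plan says this will happen.

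**Conclusion.** No change follows. The plan commits to a power analysis at a stated alpha, tied to a hypothesis about LOS, before the main randomisation. That analysis cannot be run without a difference, an SD and a power, so whoever does it must supply them. A competent analyst would take the SD from the pilot and choose the difference on clinical grounds.

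The erratic n is real only if the pilot's observed effect is used and the pilot is small. With 20 per arm and a true effect of 0.5 SD, n runs from about 19 to 515 per arm and mean power is about 71%. With 100 per arm, mean power is 78% and 6% of trials fall below 50%. The pilot's size is unknown, so no row of the table is known to apply. Under the SD-only reading the problem nearly disappears.

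The plan quotes no power that the design could miss, and the 5% test in newly randomised patients keeps its size at any n. What remains is a request to write down more detail, and no value for the LOS difference can be drawn from the documents. All figures rest on normal data, two-sided testing, 1:1 allocation and 80% nominal power, none of which the plan states.

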**Inclusion Criteria:**

Greek language speakers

Have complete mental clarity

Age >18 years

**Exclusion Criteria:**

Refusal to sign consent

Patients receiving treatment for chronic pain

Patients receiving antipsychotic therapy, Psychopathy

They have acute or chronic kidney and / or liver disease

History or family history of malignant hyperthermia

Known allergy to propofol, desflurane, or any other anesthetic agent

Impairment of cognitive function or communication

History of postoperative delirium

ERAS PROTOCOL		
Post-operation day	Informed consent Informing the patient about the ERAS program Surgical plan - Targeting Intestinal preparation with fleet-enema Thromboprophylaxis Cleaning bath	Elastic anticoagulant socks Clexane 20-40mg SC daily
Intraoperatively	Normothermia parecoxib 40mg IV paracetamol 1000mg IV Morfine 0,1mg/kg Magnesium	
Operation day, Day-0	liquids PO after 4-6 h PONV mobilization after 4 h diuresis <30 ml/h  Paracetamol 1000mg	ondansetron 4mgX2 Metoclopramide 10mgX3

	
parecoxib 40mg Morfine 0,1mg/kg
 
Diet clear fluids and jelly
	
Water, coffee, apple juice, tea

Day 1	
Mobilization out of the room Incentive spirometer Thromboprophylaxis diuresis <30 ml/h Intestinal function Cleaning bath Light Diet 1 Oxycodone / paracetamol (Depalgos) PO q: 4-6 prn Lornoxicam 8mgX2 Removal of drains
	
<30 ml/h Emollients or Senna  Diet 1: Soup, jelly, puree, boiled chicken

Day 2 & 3	
Full diet Full mobilization Incentive Spirometer Thromboprophylaxis Diuresis Intestinal function Cleaning bath Oxycodone / paracetamol (Depalgos) PO q: 4-6 prn Lornoxicam 8mgX2
	Emollients or Senna
Discharge criteria	
Full diet Full mobilization Help at home Great analgesia management Understanding the instructions
	
Discharge instructions	
Thromboprophylaxis Normal functionality of the digestive system Oxycodone / paracetamol (Depalgos) PO q: 4-6 prn
	
Follow-up	
Contact via phone Appointment for reassessment
	

NON-ERAS PATHWAYS		
Post-operation day	Intestinal preparation with fleet-enema Thromboprophylaxis Cleaning bath	Elastic anticoagulant socks Clexane 20-40mg SC daily
Intraoperatively	Normothermia parecoxib 40mg IV paracetamol 1000mg IV Morfine 0,1mg/kg	
Day 0	On nausea ondansetron 4mg X2 Mobilization at will Diuresis 30ml/h Paracetamol 1000mgX4 Tramadol 50mgX4 or Morphine 0.1mg / kg Parenteral fluid IV 2-3Lt / 24h NPO	
Day 1	Mobilization at will Thromboprophylaxis Diuresis Intestinal function Cleaning bath Diet: hydrated and jelly Paracetamol 1000mgX4 Tramadol 10mg/kgX4	
Day 2 until Discharge day	Mobilization Thromboprophylaxis Diuresis <30 ml/h Intestinal function Cleaning bath Paracetamol 1000mgX4 Tramadol 50-100mgX4 Removal of drains	emollients
Discharge criteria	Full diet Full mobilization Help at home Great analgesia management Understanding the instructions	
Discharge instructions	Thromboprophylaxis	

Follow-up	After 15 days from the surgery	
-----------	--------------------------------	--

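### The control arm's Day 1 tramadol dose is written as 10 mg/kg four times daily, which no adult weight reconciles with the fixed doses on the days either side

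*Combined protocol and SAP*

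**What the plan says.** The only detailed description of control-arm care is the NON-ERAS PATHWAYS table, which follows the exclusion criteria. Its tramadol entries are:

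- Day 0: "Tramadol 50mgX4 or Morphine 0.1mg / kg"
- Day 1: "Tramadol 10mg/kgX4"
- Day 2 until discharge: "Tramadol 50-100mgX4"

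Elsewhere the arm is described only in general terms. The Method section says that "the group B will include patients who will follow conventional postoperative care". The inclusion criteria restrict entry to patients over 18 years. The second objective, on pain levels, includes "Evaluation of analgesia and correlation of requirements with opioid analgesics".

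**The concern.** The same drug, in the same arm and at the same frequency, changes from a fixed dose to a weight-based dose for one day and then back. Day 1 is the only weight-based tramadol entry in the table. For any adult it produces a dose far above those on either side, and nothing in the protocol gives a reason for a one-day escalation, a maximum dose or a body weight.

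Two things are at stake. The first is safety: anyone who writes orders from this line would give a control patient several times the tramadol that the arm prescribes on neighbouring days. The second is the description of the comparator. Opioid requirement is part of the pain objective, and the table misstates the scheduled Day 1 opioid in the arm against which ERAS is judged.

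**Working it through.** **Inputs from the protocol (NON-ERAS PATHWAYS table).** Tramadol 50 mg × 4 on Day 0, where it is one of two options; 10 mg/kg × 4 on Day 1; 50 to 100 mg × 4 from Day 2 to discharge. I read × 4 as four doses a day. It is the same on all days, so it cancels from every ratio.

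**Input assumed.** Body weight, which the protocol does not give. I use 50 to 80 kg as the main range and 40 to 120 kg as a wide one.

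**Daily totals on the adjacent days**

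- Day 0, tramadol option: 50 × 4 = 200 mg/day.
- Day 2 onward: 50 × 4 = 200 mg/day to 100 × 4 = 400 mg/day.

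**Day 1 as written.** Dose = 10 mg/kg × weight; daily total = 4 × dose; ratio = Day 1 dose ÷ adjacent-day dose.

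| Assumed weight | Day 1 dose | Day 1 daily total | Ratio to Day 0 (50 mg) | Ratio to Day 2 onward (100 mg to 50 mg) |
|---|---|---|---|---|
| 40 kg | 400 mg | 1,600 mg | 8 | 4 to 8 |
| 50 kg | 500 mg | 2,000 mg | 10 | 5 to 10 |
| 80 kg | 800 mg | 3,200 mg | 16 | 8 to 16 |
| 120 kg | 1,200 mg | 4,800 mg | 24 | 12 to 24 |

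Over 50 to 80 kg the excess is therefore 10 to 16 times Day 0 and 5 to 16 times Day 2 onward. The low end of 5 comes only from the 100 mg upper limit from Day 2; against Day 0 the smallest ratio is 10.

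**Weight at which the lines would agree**

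- With Day 0: 50 mg ÷ 10 mg/kg = 5 kg.
- With Day 2 onward: 50 ÷ 10 = 5 kg to 100 ÷ 10 = 10 kg.

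All three entries agree only at 5 kg. This step does not depend on the assumed weights.

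**Is a Day 1 escalation signalled elsewhere?** The other analgesic on that day, paracetamol, is 1000 mg × 4 on Day 0, on Day 1 and from Day 2 onward. Nothing else in the table suggests that analgesia was meant to be stepped up for one day.

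**What would fit.** For illustration only, 1 mg/kg × 4 gives 50 to 80 mg per dose (200 to 320 mg/day) at 50 to 80 kg, and a fixed 50 to 100 mg × 4 gives 200 to 400 mg/day. Either is in line with the neighbouring days. The protocol does not say which was intended.

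**The case against.** The best argument against the point is that the figure may not be the sponsor's. The table writes an intraoperative morphine dose with a decimal comma, and a separator lost in text extraction would turn 1,0 mg/kg into 10 mg/kg. That cannot be excluded, but the entry is intact (number, unit, per-kilogram basis and frequency) and nothing around it looks damaged. It is a reason to look at the source page before amending.

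Doses may also legitimately differ between days, so the three lines are not strictly conflicting statements about one day. That is fair as logic. But a rise of at least fourfold at 40 kg, and more at higher weights, followed by a return to near the starting dose, would need an explanation, and there is none. Day 0 also offers morphine instead of tramadol, so the Day 0 ratios apply only to patients given tramadol; the comparison with Day 2 onward is unaffected.

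The table may only summarise usual care. Tramadol has no route and morphine no frequency, and nothing says that orders are generated from it. This makes the harm conditional but does not remove it, because nothing says that orders are not written from it and no maximum dose is stated.

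Finally, the effect on the trial's inference is small. The hypothesis concerns length of stay, and data are to be drawn from anaesthesia charts and patient files, so opioid use need not be inferred from this line. That stands: a misprint would mislead readers about the comparator without itself biasing the comparison of the arms.

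**Conclusion.** The concern holds. The Day 1 entry is incompatible with the rest of the control-arm tramadol schedule at any adult weight, and the likeliest explanation is a unit or decimal error. Taken literally at an assumed 50 to 80 kg, it is 5 to 16 times the adjacent days' dose; at 40 to 120 kg it is 4 to 24 times. Those multiples rest on assumed weights; the incompatibility does not.

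The entry must be corrected because it is a dose in the only detailed specification of the control arm, and acting on it would put patients at risk. The case rests on safety and on accurate description of the comparator, not on any effect on sample size, type I error or the planned analysis.

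**What to change.** Check the entry against the source page, then have the responsible clinicians confirm the intended Day 1 dose. Replace the entry with one in the same fixed-milligram form as the adjacent days, for example a dose within the 50 to 100 mg × 4 already given from Day 2, if that is what was meant. The statistician should not choose the dose.

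If control patients have already been treated, review their Day 1 tramadol orders to establish what was given.

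The cost is one table line and a short amendment, plus that chart check if it applies. Patient numbers and the analysis do not change.
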